### 3.1.4 Definition of MTD, DLT, and RP2D

#### 3.1.4.1 Definition of Maximum Tolerated Dose (MTD)

MTD is defined as the highest dose cohort at which  $\leq$  33% of patients experience BVD-523 related DLTs in the first 21 days of treatment.

#### 3.1.4.2 Definition of Dose Limiting Toxicity (DLT)

DLT is defined as BVD-523 related toxicity in the first 21 days of treatment that results in:

- $\geq$  Grade 4 hematologic toxicity for > 1 day

- Grade 3 hematologic toxicity with complications e.g., thrombocytopenia with bleeding
- $\geq$  Grade 3 non-hematologic toxicity, except untreated nausea, vomiting, constipation, pain, and rash (these become DLTs if the AE persists despite adequate treatment), a doubling of AST/ALT in patients with grade 2 ALT/AST at baseline
- A treatment interruption exceeding 5 days (or an interruption exceeding 7 days for rash, despite adequate treatment) in Cycle 1 (or inability to begin Cycle 2 for > 7 days) due to BVD-523-related toxicity

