##### 3.1.2 Study Design

This clinical study comprises 2 parts:

- Part 1: Dose-escalation Phase
- Part 2: Cohort Expansion Phase

Part 1 – Dose-escalation Phase: An accelerated dose escalation plan will be used to establish dose limiting toxicities (DLT), maximum tolerated dose (MTD), and the recommended Phase 2 dose (RP2D). One to 6 patients per treatment cohort will be assigned to receive sequentially higher oral doses of BVD-523 on a twice daily schedule (b.i.d.) for 21 days (a “Cycle”), starting at a dose of 10 mg twice daily. Patients will receive twice-daily oral doses of BVD-523 until disease progression, unacceptable toxicity, or a clinical observation satisfying another withdrawal criterion is noted. Treatment cycles will occur consecutively without interruption, except when necessary to manage toxicities.

Patients with advanced-stage solid tumors only (no hematological malignancies) will be enrolled in the dose-escalation phase of the study. The study will initially be conducted as an accelerated single patient design, followed by a standard 3 + 3 design, informed by the

accrued safety experience throughout the study (see Table 3.2 below). All dose-escalation decisions will be based on Cycle 1 safety data.

In the accelerated single patient phase, 1 patient will be enrolled in a cohort and an evaluation of dose escalation will take place after the patient has completed the 21-day treatment cycle. If the patient exhibits no Grade 2 or greater adverse events, dose escalation in a 100% increment and enrollment will continue with a single patient per cohort. However, when one patient experiences a  $\geq$  Grade 2 toxicity (excluding alopecia or diarrhea), this cohort and subsequent cohorts will be expanded to at least 3 patients each following the classic 3 + 3 design and dose escalation increments will be reduced from 100% to a maximum of 50%, as determined by discussion with the Clinical Investigators, the Medical Monitor, and the Sponsor. Doses will not be escalated unless the patient(s) receiving the highest current dose has been observed for at least 3 weeks.

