The classic 3 + 3 design will be conducted as follows. Initially, 3 patients will be enrolled to a cohort; the occurrence of a single drug-related DLT in one of these 3 patients will prompt enrollment of up to an additional 3 patients to that same cohort i.e., 3 + 3. When more than 1 DLT occurs in  $\leq$  6 patients in a dosing cohort, dose escalation will be stopped and this dose level will be identified as the non-tolerated dose. Doses between the non-tolerated dose and the preceding lower dose, where  $\leq$  1 DLT occurred, may be explored to define the MTD. This strategy allows for a rigorous determination of MTD, especially if the dose increase that resulted in determination of the non-tolerated dose is relatively large (i.e.,  $>$  50%).

At any time during the study, the Sponsor and Investigators may request that cohorts should be enlarged or that exploration of intermediate doses between 2 planned escalation steps should be explored. Such requests will be discussed with the Sponsor and Medical Monitor, and should be based on all data existing at that time, including determinations of pharmacokinetics, pharmacodynamics, and cumulative toxicity. Before each escalation, investigators will be consulted to ensure that all involved agree with the escalation decision.

In addition, once the RP2D is defined, intra-patient dose escalation to the RP2D will be allowed after a patient has completed at least 1 cycle at their assigned dose and only if the patient has experienced no toxicity above Grade 1, upon request by the PI and discussion with the Medical Monitor and the Sponsor.

Part 2 – Cohort-expansion Phase: Additional patients with particular tumor types and/or cancers harboring specific genetics will be recruited for treatment at the Recommended Phase 2 Dose (RP2D). Patients must have measurable disease by RECIST 1.1. Patients will receive twice daily oral doses of BVD-523 in 21-day treatment cycles until disease progression, unacceptable toxicity, or another withdrawal criterion is met (Section 7.2). Treatment cycles will occur consecutively without interruption except when necessary to manage toxicities.

Total enrollment for Part 2 is targeted at approximately 105 evaluable patients. Patients will be enrolled into 1 of 7 treatment groups. Group assignments are made according to the following disease characteristics, which correspond to specific inclusion and exclusion criteria for Part 2.

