### 3.1.3 Summary of Dose Escalation

**Table 3.2. Summary of Dose Escalation**

Observed Safety Outcomes	Action
Single Patient Cohorts	
AEs $\leq$ Gr 1	
 
Continue testing with single patient cohorts
 
Escalate by 100% to next dose level
 

One AE $\geq$ Gr 2 (excluding alopecia or diarrhea)	
 
Expand current and subsequent cohorts to <math>\geq</math> 3 patients
 
Escalate by <math>\leq</math> 50% to next dose level
 

1 DLT	
 
Expand cohort up to 6 patients
 

Standard Escalation Cohorts (3–6 patients)	
No DLTs	
 
Escalate by <math>\leq</math> 50% to next dose level
 

1 DLT in 3 patients	
 
Expand cohort up to 6 patients
 

1 DLT in 6 patients	
 
Escalate by <math>\leq</math> 50% to next dose level
 

> 1 DLT in $\leq$ 6 patients	
 
Stop dose escalation
 

*Note:* DLT (see Section 3.1.4.2) is defined as any BVD-523 related toxicity in the first 21 days of treatment that results in:

- $\geq$  Grade 4 hematologic toxicity for > 1 day
- Grade 3 hematologic toxicity with complications e.g., thrombocytopenia with bleeding
- $\geq$  Grade 3 non-hematologic toxicity, except untreated nausea, vomiting, constipation, pain and rash (these become DLTs if the AE persists despite adequate treatment), a doubling of AST/ALT in patients with grade 2 ALT/AST at baseline
- A treatment interruption exceeding 5 days (or an interruption exceeding 7 days for rash, despite adequate treatment) in Cycle 1 (or inability to begin Cycle 2 for > 7 days) due to BVD-523-related toxicity.

Each cohort can only begin when the previous cohort has completed treatment to at least the end of Week 3 without fulfilling a criterion that would prevent dose escalation.

Although dose escalation decisions may be taken upon review of the data from Cycle 1, safety data will be collected from all patients continuing treatment and reviewed periodically by the Safety Monitoring Committee. Any detected cumulative toxicity may require later dose reductions or other action as appropriate, including having an effect on the RP2D.

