### 5.2.5 Visit 5 (Day 22 ± 1 of Cycle 1, first day of Cycle 2)

- Review medical history including all cancer treatments received since previous visit.
- Record medications including start/stop dates, indication, dose and frequency taken after Visit 4.
- Perform and record targeted physical examination as appropriate.
- Assess and record performance status (ECOG).
- Record vital signs. Measure body temperature, systolic/diastolic BP and pulse rate.
- Obtain all unused study drug from patient.
- Assess study drug compliance by reviewing pill count.
- Collect blood samples for blood chemistries, hematology and creatinine clearance.
- Collect urine samples for urinalysis.
- Perform urine pregnancy test for female patients who are not postmenopausal or surgically sterile. If urine test is positive, collect blood for a serum pregnancy test.
- Collect a pre-dose blood sample for pharmacokinetic analyses.
- Administer BVD-523 and dispense drug supply for self-dosing for Cycle 2 if appropriate.
- Assess and record disease status, including safety, pharmacokinetics, and pharmacodynamics.
- Assess and record AEs.
- For patients who have given consent for optional research tests involving the collection of plasma samples for circulating tumor DNA analysis, collect plasma samples.

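### The next dose level can open at the end of Week 3, about a week before the Cycle 2 delay criterion for a DLT can be known (narrow gap, cheap to close)

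*Protocol*

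**What the plan says.** **The DLT definition.** Protocol 3.1.4.2, repeated under Table 3.2 and in SAP 2.1.1 and 10.2, requires a drug-related toxicity in the first 21 days of treatment with one of several consequences. One consequence is "inability to begin Cycle 2 for > 7 days". The others are severity criteria and a Cycle 1 interruption of more than 5 days (more than 7 for rash).

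**When Cycle 2 starts.** Protocol 5.2.5 is headed "Visit 5 (Day 22 ± 1 of Cycle 1, first day of Cycle 2"). At that visit the site is to "Administer BVD-523 and dispense drug supply for self-dosing for Cycle 2 if appropriate", so a hold would be visible there.

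**The escalation gates.** Protocol 3.1.2 says "Doses will not be escalated unless the patient(s) receiving the highest current dose has been observed for at least 3 weeks", and SAP 3.1 repeats it. The note to Table 3.2, repeated in 8.1.2, says "Each cohort can only begin when the previous cohort has completed treatment to at least the end of Week 3", provided that no criterion preventing escalation has been fulfilled. Section 8 asks for three weeks of observation and fewer than 2 of 6 patients with reported dose-limiting effects.

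**The discretionary checks.** Section 3.3 places a safety review before each new dose level. Section 3.1.2 adds that "investigators will be consulted to ensure that all involved agree with the escalation decision". Neither states a follow-up time or says how to count a patient whose Cycle 2 start is pending.

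**The concern.** One listed consequence that makes a toxicity a DLT cannot be observed by the time the written gate can be satisfied. A patient who takes drug through Day 21 and is then held has been observed for three weeks, has been treated to the end of Week 3, and has no DLT reported yet. If the rest of the cohort is clear, the text permits the next dose level to open, although this patient may be classified as a DLT about a week later.

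In a 3+3 design the action turns on single events. An escalation made on an incomplete count puts new patients on a dose up to 50% higher when the complete count would have called for expanding the current cohort or stopping. Such holds are plausible. Section 8 interrupts treatment for unacceptable toxicity until it returns to Grade 1 or baseline, and 1.4 reports that rash and gastrointestinal events have been managed with dosing interruptions.

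**Working it through.** **Inputs**
- Cycle 2 due: Day 22, visit window ± 1 day (protocol 5.2.5).
- Delay limit: more than 7 days (3.1.4.2).
- Gate: 3 weeks, or end of Week 3 (3.1.2, Table 3.2 note, 8, 8.1.2).
- Cycle 1 interruption limit: more than 5 days, or more than 7 for rash (3.1.4.2).
- Dose step in standard cohorts: at most 50% (Table 3.2).

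**1. The plan's own calendar.** A 21-day cycle starting on Day 1 puts Cycle 2 on 21 + 1 = Day 22, as stated. The gate falls at 3 × 7 = Day 21, so the next cohort can open from Day 22.

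**2. When the delay criterion is first met.** A delay of exactly 7 days does not qualify. The first qualifying day is the due day + 8.

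| Cycle 2 due | Exactly 7 days late | First day more than 7 days late | Days after Day 22 |
|---|---|---|---|
| Day 21 | Day 28 | Day 29 | 7 |
| Day 22 | Day 29 | Day 30 | 8 |
| Day 23 | Day 30 | Day 31 | 9 |

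A patient who starts Cycle 2 before then is settled earlier, as not a DLT by this criterion.

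**3. Which holds are affected.** A hold starting on Day s and lasting through Day 21 has run 22 − s days.
- It exceeds 5 days if s ≤ 16 (22 − 16 = 6). For rash it exceeds 7 days if s ≤ 14 (22 − 14 = 8). These holds are already DLTs under the interruption criterion.
- Holds starting on Days 17 to 21 (15 to 21 for rash) are not yet DLTs, but they arguably fail the Table 3.2 condition that treatment was completed to the end of Week 3.
- A patient dosed through Day 21 and held from Day 22 passes every gate. This is the clear case.

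The toxicity must also meet no other DLT criterion. That leaves mainly Grade 2 events, uncomplicated Grade 3 hematologic toxicity, and the events excepted from the Grade 3 rule (nausea, vomiting, constipation, pain, rash).

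**4. Position in the cohort.** If Cycle 2 is due on Day 22, the held patient is classified by Day 30. The last patient in the cohort reaches Day 22 on or after that date if the held patient started at least 30 − 22 = 8 days earlier. The gap exists only when the held patient started fewer than 8 days before the last patient, or is the last.

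**5. Effect of one pending DLT (Table 3.2)**

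| Count at the gate | Action | Count once confirmed | Action |
|---|---|---|---|
| 0/3 | Escalate by up to 50% | 1/3 | Expand to up to 6 |
| 1/6 | Escalate by up to 50% | 2/6 | Stop |

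**6. Single-patient cohorts.** These are largely protected. After a toxicity of Grade 2 or more (other than alopecia or diarrhea), "this cohort and subsequent cohorts will be expanded to at least 3 patients each".

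**7. No probability is calculated.** The documents give no rate for DLTs that become known only through a Cycle 2 delay.

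**The case against.** The strongest reply is that the point is close to moot. SAP 15 records that the Part 1 SAP was finalized under amendment 4. SAP 10.2 introduces the current DLT definition as the one for Part 2, and the Part 2 listings include the RP2D carried over from Part 1. Part 2 patients start at the RP2D under a separate stopping rule, so this gate does not apply to them. Section 3.1.2 still allows "exploration of intermediate doses between 2 planned escalation steps should be explored" at any time, but after a stop such doses lie below one already given, where the exposure concern is weaker.

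The existing text also helps. Three weeks is a minimum. A cohort with an unresolved criterion arguably has neither no DLTs nor one in six. The safety review is mandatory, investigators must agree, and the hold is visible at Visit 5. In practice, review and enrollment might take up the extra week anyway.

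Most of this stands and sets the severity. It does not remove the gap: these checks permit waiting without requiring it, no sentence says how to count a pending patient, and the escalation rules remain in the current protocol.

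A reader might go further and infer that the protocol forces escalation on incomplete data. It does not; it only allows it.

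**Conclusion.** The gap is real, narrow and of low severity. A stated gate can close before a stated DLT criterion can be known, by about 8 days (7 to 9 across the visit window). The gap is clear only for the patient described in steps 3 and 4 of the working. One such patient is enough to change the action, and the dose step at risk is at most 50%.

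Two stronger readings are tempting, and the documents support neither.
- **A wrong final MTD.** The 21-day limit in 3.1.4.2 attaches to the toxicity, while its consequence may fall later; otherwise the Cycle 2 clause could hardly ever apply. A DLT confirmed after Day 21 therefore still counts toward the MTD. The harm is avoidable exposure for a short period.
- **A calculable rise in the chance that an unsafe dose passes.** That needs a rate of late-classified DLTs and an assumption that they are never added back. The first is not in the documents, and the second contradicts the definition.

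The conclusion assumes that more than 7 days is counted in whole days from the scheduled Cycle 2 start. That Part 1 escalation is complete is inferred from the SAP, not stated outright. If it is complete, the point matters only for a further dose level opened under these rules.

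**What to change.** Add one sentence to the gate under Table 3.2, and to the matching text in 3.1.2, 8 and 8.1.2:

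> The next dose level may not open until every patient counted in the current cohort has started Cycle 2, had a DLT, been delayed more than 7 days past the scheduled Cycle 2 start (and so been classified), or come off treatment for a reason other than BVD-523-related toxicity.

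Repeating it in the SAP is optional, because SAP 1 refers to the protocol for study conduct.

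The cost is one sentence of protocol wording, plus a wait of about 8 to 9 days when a patient in the cohort is on hold at Day 22. The wait is shorter if that patient restarts sooner or started earlier than the others. A cohort whose patients all start Cycle 2 on time is not held up beyond that visit.

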#### 3.1.4.3 Definition of Recommended Phase 2 Dose (RP2D)

The Recommended Phase 2 Dose (RP2D) may be as high as the MTD and will be determined in discussion with the Clinical Investigators, the Medical Monitor, and the Sponsor. Observations related to pharmacokinetics, pharmacodynamics, and any cumulative toxicity observed after multiple cycles may be included in the rationale supporting the RP2D.

### 3.2 SAFETY MONITORING COMMITTEE

An internal Safety Monitoring Committee (SMC) will be set up to review the safety of BVD-523 as the study progresses. The SMC will consist of Clinical Investigators, the Medical Monitor and BVD representatives. The SMC will review any serious Adverse Event (SAE) that occurs during the study, and will examine the safety of each dose level of BVD-523, including toxicities that may occur in later cycles of treatment.

### 3.3 SAFETY REVIEW MEETINGS

The safety review will be performed in all stages of the dose escalation:

1. Prior to starting each new dose level after the initial cohort.
2. To stop the dose escalation if the MTD has been reached.

### 3.4 STOPPING RULES

The entire study or treatment of individual patients may be stopped under defined circumstances as outlined in Section 7.

### 3.5 STUDY ENDPOINTS

#### 3.5.1 Primary Endpoint(s)

##### Safety

- Evaluation of the DLTs of BVD-523
- Determination of MTD of BVD-523
- Determination of RP2D of BVD-523
- Evaluation of treatment-related AEs of BVD-523

### 3.5.2 Secondary Endpoint(s)

#### Pharmacokinetics

- Evaluation of pharmacokinetic parameters of BVD-523 and selected metabolites in patients with advanced malignancies.

#### Efficacy

- Preliminary clinical effects on tumor response assessed by physical or radiological exam (RECIST 1.1).

### 3.5.3 Exploratory Endpoint(s)

#### Pharmacodynamics

- Evaluation of multiple biomarkers to characterize response to drug (pRSK, pERK, Ki67, Caspase-3, and circulating tumor DNA). Additional biomarkers may be identified and measured as appropriate. Tumor genotyping by DNA analysis will be performed to identify somatic alterations, relying on either available archived tissue or freshly-collected samples.

## 3.6 BLINDING AND RANDOMIZATION

This study is designed as an open-label study. All patients will receive treatment with orally administered BVD-523.

## **4 SELECTION OF PATIENTS**

### **4.1 NUMBER OF PATIENTS**

In this Phase 1 study up to 40 patients with advanced solid tumors will be enrolled in Part 1. One to six patients per treatment cohort will be assigned to receive sequentially higher oral doses of BVD-523.

The purpose of Part 2 of this first in human research is to document that there is some evidence of a response. Upon completion of Part 1 of this study, up to approximately 105 evaluable patients with certain cancer types and/or characterized genetics will be assigned to 1 of 7 treatment arms and treated with the RP2D determined in Part 1 (which may be the same or lower than the MTD). The observation of DLTs in more than 33% of patients in any Part 2 cohort with at least 6 patients enrolled at any time during Part 2 will trigger temporary stopping of patient enrollment and revision of the definition of the MTD and potentially RP2D in the specific cohort. Subsequent patients will be treated with a dose lower than the initial MTD and this dose will be determined in discussion with the Clinical Investigators, the Medical Monitor, and the Sponsor.

Enrollment of up to 15 evaluable patients in each cohort provides an 80% probability of seeing at least one positive response if the true response rate is at least 10%. Allowing for a low response rate in these patient cohorts is appropriate based on unmet medical need.

In Part 2 of the study, patients who withdraw at any time preceding the 1st protocol-specified tumor measurement evaluation at the end of Cycle 2 (except for study drug-related AE) will be replaced.

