Statistical Methods: 
The sample size for Part 1 of this study was determined by clinical rather than statistical considerations. Approximately 40 patients will be treated in Part 1 of this study (Dose Escalation Phase) to establish dose limiting toxicities (DLT), maximum tolerated dose (MTD), and the recommended Phase 2 dose (RP2D).
 
The purpose of Part 2 of this first in human research is to document that there is some evidence of a response. Upon completion of Part 1 of this study, up to approximately 105 evaluable patients with certain cancer types and/or characterized genetic alterations will be treated with the RP2D (which may be the same or lower than the MTD). The observation of DLTs in more than 33% of patients in any Part 2 cohort with at least 6 patients enrolled at any time during Part 2 will trigger temporary stopping of patient enrollment and revision of the definition of the MTD and potentially RP2D in the specific cohort. Subsequent patients will be treated with a dose lower than the initial MTD and this dose will be determined in discussion with the Clinical Investigators, the Medical Monitor, and the Sponsor.
 
Enrollment of up to 15 evaluable patients in each cohort provides an 80% probability of seeing at least one positive response if the true response rate is at least 10%. Allowing for a low response rate in these patient cohorts is appropriate based on unmet medical need.
		

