#### **10.1.2 Determination of Sample Size**

The sample size for Part 1 of this study was determined by clinical rather than statistical considerations. Approximately 40 patients will be treated in Part 1 of this study (Dose Escalation Phase) to establish dose limiting toxicities (DLT), maximum tolerated dose (MTD), and the recommended Phase 2 dose (RP2D).

The purpose of Part 2 of this first in human research is to document that there is some evidence of a response. Upon completion of Part 1 of this study, up to approximately 105 evaluable patients with certain cancer types and/or characterized genetic alterations and/or MAPK pathway activation will be treated with the RP2D (which may be the same or lower than the MTD). The observation of DLTs in more than 33% of patients in any Part 2 cohort with at least 6 patients enrolled at any time during Part 2 will trigger temporary stopping of patient enrollment and revision of the definition of the MTD and RP2D in the specific cohort. Subsequent patients will be treated with a dose lower than the initial RP2D and this dose will be determined in discussion with the Clinical Investigators, the Medical Monitor, and the Sponsor.

Enrollment of up to 15 evaluable patients in all cohorts provides an 80% probability of seeing at least one positive response if the true response rate is at least 10%. Allowing for a low response rate in these patient cohorts is appropriate based on unmet medical need.

Up to 15 study centers are expected to enroll patients for this study.

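### After too many DLTs in a Part 2 cohort, the Synopsis and Section 4.1 cap later doses below the initial MTD, but Section 10.1.2 caps them below the initial RP2D; if RP2D < MTD, the looser cap permits the same dose

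*Protocol*

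**What the plan says.** The same Part 2 safety rule appears three times in the protocol: in the Synopsis (Statistical Methods), in Section 4.1 and in Section 10.1.2. The trigger is the same each time: DLTs in more than 33% of patients in a cohort with at least 6 enrolled, which "at any time during Part 2 will trigger temporary stopping of patient enrollment". The consequences differ.

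- **Synopsis and Section 4.1.** The rule calls for "revision of the definition of the MTD and potentially RP2D in the specific cohort", and then: "Subsequent patients will be treated with a dose lower than the initial MTD".
- **Section 10.1.2.** The rule calls for "revision of the definition of the MTD and RP2D in the specific cohort", and then: "Subsequent patients will be treated with a dose lower than the initial RP2D".

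In all three places the new dose is settled among the Clinical Investigators, the Medical Monitor and the Sponsor. Section 4.1 says Part 2 patients are "treated with the RP2D determined in Part 1 (which may be the same or lower than the MTD". Section 3.1.4.3 says the same of the relation between the two doses: "The Recommended Phase 2 Dose (RP2D) may be as high as the MTD". The SAP does not restate the rule.

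**The concern.** The dose given in Part 2 is the RP2D, so a rule that responds to excess toxicity in Part 2 should be anchored to the RP2D. A ceiling anchored to the initial MTD forces a reduction only if the two doses are equal. Section 3.1.4.3 lets pharmacokinetics, pharmacodynamics and cumulative toxicity inform the RP2D, and any of these could place it below the MTD. In that case the Synopsis and Section 4.1 ceiling is met by the very dose that stopped enrollment, and by any dose between it and the MTD.

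What is at stake is the dose for the next patients in a cohort whose observed DLT rate has just passed 33%. A reader of the Synopsis or Section 4.1 sees the looser ceiling; the stricter one stands under the sample-size heading.

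**Working it through.** **Comparing the ceilings.** Let M be the initial MTD and R the initial RP2D, with R ≤ M. The triggering dose is R.

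| Case | Synopsis and 4.1: dose < M | 10.1.2: dose < R |
|---|---|---|
| R = M | excludes R | excludes R |
| R < M (for example M = 100, R = 80, assumed units) | admits R and any dose from 80 up to, but not including, 100 | excludes R and everything above it |

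The ceilings nest: any dose below R is also below M. A dose that meets Section 10.1.2 therefore meets all three places, and keeping R breaches Section 10.1.2.

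**The plan's own figures.** The documents give no operating figures for this rule. The only computed figure beside it is the 80% chance of at least one response in 15 patients at a 10% response rate. It reproduces: 1 − 0.9^15 = 0.794. The present point does not depend on it.

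**Illustration of size (applies only if R < M).** The assumptions are independent patients, one look after each patient from n = 6 to n = 15, and counts cumulated within the cohort. The true DLT rates p are assumed. The threshold can be read as > 0.33, so that 2 of 6 triggers, or as > 1/3, so that it does not; results for the second reading are in brackets.

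- Smallest DLT count that triggers, > 0.33: 2 at n = 6; 3 at n = 7–9; 4 at n = 10–12; 5 at n = 13–15.
- Smallest DLT count that triggers, > 1/3: 3 at n = 6–8; 4 at n = 9–11; 5 at n = 12–14; 6 at n = 15.

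Exact sequential binomial probability that a cohort of up to 15 triggers:

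| p | > 0.33 | > 1/3 |
|---|---|---|
| 0.20 | 0.420 | 0.254 |
| 0.30 | 0.711 | 0.560 |
| 0.40 | 0.896 | 0.811 |

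Now suppose that after a trigger the dose stays at R, p = 0.40, and the rule is still applied after each patient.

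- Mean further patients until the threshold is exceeded again or n = 15: 1.762 (1.287).
- Further DLTs: 0.40 × 1.762 = 0.705 (0.40 × 1.287 = 0.515).
- Excess over a reduced dose with a 20% DLT rate: (0.40 − 0.20) × 1.762 = 0.352 (0.257).
- Excess over a reduced dose with a 30% DLT rate: (0.40 − 0.30) × 1.762 = 0.176 (0.129).

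If the rule were never applied again after the first trigger, the mean number of remaining patients would be 8.344 (7.701), and the further DLTs 0.40 × 8.344 = 3.34 (3.08). That is an outer bound, not the expected course.

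**The case against.** The strongest reply is that the protocol read as a whole already requires a reduction. The Synopsis and Section 4.1 make revision of the cohort MTD mandatory. Section 3.1.4.1 begins "MTD is defined as the highest dose cohort at which" and sets the limit at 33% of patients with DLTs. If toxicity does not fall with dose, a revised MTD should lie below a dose that exceeded that limit, and Section 3.1.4.3 keeps the RP2D no higher than the MTD. This stands as evidence that a reduction was intended. It does not repair the stated ceiling, for two reasons. The ceiling refers to the initial MTD, so revising the MTD does not tighten it. The word placed before RP2D in those two places also leaves open an unchanged RP2D, which Section 10.1.2 does not.

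A second reply is that nobody is forced to choose, because the ceilings nest and no site sets the dose alone. That is correct and limits the harm. Other safeguards limit it too:

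- The Safety Monitoring Committee examines each dose level (Section 3.2).
- Cumulative toxicity may lead to dose reductions or affect the RP2D (Sections 3.1.3 and 8.1.2).
- Related death or anaphylaxis suspends the study (Section 7.1).
- A patient with a DLT has treatment interrupted and possibly reduced (Sections 8 and 8.1.2).

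None of these four sets a ceiling for the next patients in the affected cohort.

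Third, the problem exists only if RP2D < MTD, and the illustration describes conduct that Section 10.1.2 forbids, at assumed rates. It also takes each patient's 21-day DLT window as complete before the next look. All of this is true, which is why the figures indicate scale only.

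**Conclusion.** The concern holds. One safety rule has two different dose ceilings and two different statements of what must be revised, and the SAP does not settle which applies. The looser version is wrong as written whenever RP2D < MTD, because it is already satisfied by the dose that triggered the stop. If RP2D = MTD there is no difference.

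The rules are inconsistent rather than irreconcilable, and re-dosing at the same level is unlikely in practice. Under the stated assumptions the cost of doing so is about 0.13 to 0.35 excess DLTs per triggered cohort, taking both readings of the threshold and reduced-dose rates of 20% and 30%. Confidence in the textual mismatch is high. It should be fixed because it governs dosing after excess toxicity; it has no bearing on sample size or error rates.

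**What to change.** In the Synopsis (Statistical Methods) and Section 4.1, replace the ceiling sentence with the Section 10.1.2 wording, "Subsequent patients will be treated with a dose lower than the initial RP2D", and the revision clause with "revision of the definition of the MTD and RP2D in the specific cohort". The documents do not say which version was intended, so the sponsor should confirm. The Section 10.1.2 version is preferable because a dose that meets it satisfies all three places whether or not RP2D equals MTD.

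The cost is two sentences in each of two places, by protocol amendment. No endpoint, sample size or analysis changes. The downside is that a chance trigger at an acceptable dose also forces a reduction. At a true DLT rate of 20% (assumed) a cohort of 15 triggers with probability 0.420 (0.254), which is 7 × 0.420 = 2.94 (7 × 0.254 = 1.78) groups if all seven fill to 15 at that rate. Section 10.1.2 already requires the reduction in those cases, so the change adds no new obligation.
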